#### **5.13.8.3. Eye Examination**

Summary statistics will be produced for the following continuous parameters: thickness and volume of eye retinal thickness grid for each left and right eye: left eye total visual acuity score, right eye total visual acuity score (scores expressed as logMAR calculated as the negative log (base 10) of the decimal scores), as well as left eye intraocular pressure and right eye intraocular pressure (both in mmHg). In addition, summary statistics for the difference of maximum value during treatment minus baseline value for left eye total visual acuity score, right eye total visual acuity score, left eye intraocular pressure (mmHg), and right eye intraocular pressure (mmHg) will also be produced.

In order to assess any changes/deteriorations during treatment, number and proportion of subjects with any treatment-emergent abnormal finding (in slit lamp examination, dilated fundus examination, color vision examination, fundus photography and ocular coherence tomograph) will be summarized by visit and at any time during treatment period, and compared among treatment groups using Fisher exact test. Treatment-emergent abnormal findings include any

“new” or “worsened” findings in slit lamp, dilated fundus, and color vision exams, and any severity category increase in fundus photography and ocular coherence tomograph parameters at any post-baseline visits. Potentially clinically significant findings in slit lamp, dilated fundus, and color vision exams will also be summarized separately.

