ADCS-ADL			X								X							X		X
FAQ			X								X							X		X
MMSE ^f	X										X							X		X
ECog			X								X							X		X
NPI			X															X		X
BASQID			X															X		X
Imaging Measures ^{c,g}																				
MRI	X																	X		X
Florbetapir PET (including perfusion)	X																	X		X
¹⁸ F-AV-1451 PET		X																X^h		X^h
Laboratory Measures																				
Urinalysis	X		X					X			X			X				X		X
Blood sample for APOE genotyping		X																		
Blood sample for pharmacogenetics		X																		

Study Procedure		reening Period									Do	uble E	Blind	Perio	1					
Visit ^a	V1 ^b	V2	V3	V4	V5	V6	V7	V8	V9	V10	V11	V12	V13	V14	V15	V16	V17	V18	Follow Up	ED ^c
Week	-6	0 to -1 ^d	0	1	2	4	8	12	16	20	24	28	32	36	40	44	48	52	56	,
Tolerance Interval (days)				±5	±5	±7	±7	±7	±7	±7	±7	±7	±7	±7	±7	±7	±7	±10	±10	
Blood sample for epigenetics		X																X		
Blood sample for RNA ⁱ		X																X		
Plasma LY3202626 (PK) ^j					X^k	X^k	X^{l}	X^k	X^{l}		X^{m}									X
Plasma peptides: $A\beta_{1-40}$, $A\beta_{1-42}$, $A\beta_{1-x}$ (PD) ⁿ		X			X	X	X	X	X		X							X		X
Plasma samples (EDTA) for storage and exploratory biomarker R&D		X				X	X	X	X	X	X			X				X		X
Clinical Chemistry, Hematology, Electrolytes ^o	X		X		X	X	X	X	X	X	X			X				X	X	X
Safety Measures																				
Eye Examination ^p	X							X					X					X		X
Skin Examination ^q	X							X			X							X		X
Physical/Neurological Examination	X		X		X		X			X				X				X		X
Vital Signs ^r	X	X	X	X	X	X	X	X	X	X	X	X	X	X	X	X	X	X	X	X
Height	X																			
Body weight	X							X			X							X		X
12-lead ECG(triplicate)	Xs		X	X		X	X		X		X		X		X			X	X	X
C-SSRS ^t /Self Harm Supplement Form	X	X	X	X	X	X	X	X	X	X	X	X	X	X	X	X	X	X	X	X
Dispense Drug			X^{u}			X	X	X	X	X	X	X	X	X	X	X	X			
Assess Drug Compliance				X	X	X	X	X	X	X	X	X	X	X	X	X	X	X		X
Adverse Events		X	X	X	X	X	X	X	X	X	X	X	X	X	X	X	X	X	X	X

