9.4.5.2. Eye Examination

All patients will undergo comprehensive eye examinations performed under the supervision of an optometrist or ophthalmologist to assess visual function and morphology. Scheduled examinations will include the following: visual acuity, intraocular pressure, dilated funduscopic exam (dilation only performed in patients without contraindication to mydriatics), slit lamp exam, color photography of the retina, and optical coherence tomography (OCT) or equivalent; examinations may also include color vision assessment where feasible. Assessments will be performed at times shown in the Schedule of Activities (Section 2), preferably supervised by the same optometrist or ophthalmologist for each patient's visit. Patients who complain of vision disturbance, such as change in field of vision, color, acuity or anything potentially localizable to the retina, during the clinical trial should be referred to the optometrist or ophthalmologist for unscheduled evaluation

Data from the eye examination visits will be provided from the local optometrist or ophthalmologist to the Investigator. Based on the morphological and functional results, the investigator will include or exclude the patient in consultation with the performing eye examiner, if applicable.

The local optometrist or ophthalmologist will review the color photography and OCT to aid in the investigator's assessment of study eligibility and for immediate patient management. Additionally, the color photography of retina and OCT will be analyzed by a central reader.

Unblinded results of the eye safety data will be reviewed by the Assessment Committee (AC) with the participation of an ophthalmologist, as specified in Section 10.3.7.

Any clinically significant findings that result in a diagnosis should be reported to Lilly or its designee as a pre-existing condition or AE via eCRF per Section 9.2. The PI will make all final determinations of AEs in consultation with performing eye examiner, if applicable.

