10.3.4. Safety Analyses

Safety will be assessed by summarizing and analyzing AEs, laboratory analytes, vital signs, ECGs, skin examinations, and eye examinations during the treatment period. For continuous safety measurements, a change from baseline will be analyzed using an MMRM or an ANCOVA model.

Safety analyses for the treatment period will include comparisons between LY3202626 dose groups and placebo. All hypotheses will be tested at a 2-sided α =.05 significance level. No adjustments for multiple comparisons will be made.

For analysis comparing proportion of treatment-emergent abnormalities between treatment groups for laboratory analytes, vital signs, weight, ECGs, skin examinations, and eye examinations, only patients who have both a baseline observation and a postbaseline observation will be included in the analysis for each analyte or parameter, respectively. The proportion of patients with abnormalities will be summarized and compared between treatment groups using Fisher's exact test.

Suicide-related thoughts and behaviors, based on the C-SSRS, will be listed by patient and visit. Only patients that show suicidal ideation/behavior will be displayed (that is, if a patient's answers are all "no" for the C-SSRS, then that patient will not be displayed). However, if a

patient reported any ideation or behavior at any time point, then all their ideation and behavior will be displayed, even if not positive.

Additional safety analyses may be performed if warranted.

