### 3. Revision History

Statistical Analysis Plan (SAP) Version 1 was approved prior to unblinding.

Statistical Analysis Plan (SAP) Version 2 was approved prior to final database lock. Due to early termination of the study, certain analyses were removed or simplified, while others were clarified. The changes in SAP version 2 are summarized below:

- Clarified that change from baseline to last observation is to be used in ANCOVA analysis if Week 52 observation is not available (Section [5.1](#))
- Removed the exploratory analysis on subjects with study partner change during the study (previously Section 5.11 in Version 1)
- Clarified the analysis for changes from baseline in NPI total score and BASQID total score will be ANCOVA instead of MMRM because they were collected only once during post-baseline visits (Section [5.11.2](#))
- Specified the cut-off for defining Tau subgroups and removed the subgroup analysis regarding race and country (Section [5.11.3](#))
- Removed sensitivity analysis on Tau PET using percentage changes from baseline (previously Section 5.12.4 in Version 1)
- Simplified analysis of CSF biomarkers to listing of values by visit by treatment due to very limited number of subjects participated in the CSF addendum (Section [5.12.2](#))
- Added analysis on annualized change in imaging biomarkers (vMRI, AV-45 PET, AV-1451 PET) because majority of the subjects would not have Week 52 observation due to early termination of the study (Section [5.12.5](#))
- Added an incidence summary for treatment-emergent CSSRS findings (Section [5.13.8.1](#))
- Simplified and clarified the analysis for categorical eye exam and eye imaging data (Section [5.13.8.3](#))

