## 5. A Priori Statistical Methods

### 5.1. General Considerations

All tests of treatment effects of biological efficacy or clinical efficacy will be conducted at a 1-sided  $\alpha=.10$ , unless otherwise stated. Safety assessments will be conducted at a 2-sided  $\alpha=.05$ .

A repeated measures analysis refers to a restricted maximum likelihood (REML)-based, mixed effects repeated measures analysis using all the longitudinal observations at each post-baseline visit.

All analyses will follow the intent-to-treat (ITT) principle unless otherwise specified. An ITT analysis is an analysis of data by the groups to which subjects are assigned by random allocation, even if the subject does not take the assigned treatment, does not receive the correct treatment, or otherwise does not follow the protocol.

When change from baseline is assessed, subjects will be included in the analysis only if both a baseline and a postbaseline measure are available. Unless otherwise defined, Visit 3 is the baseline visit, and baseline value is defined as last value available before or at Visit 3.

All total and subscale scores will be derived from individual items. If any individual item is missing, the corresponding total and subscale scores will be considered missing, except for the ADAS-Cog13 and ADCS-iADL, which will be imputed.

A repeated measures analysis model will include the fixed, categorical effects of treatment, visit, and treatment-by-visit interaction, as well as the continuous, fixed covariates of baseline, baseline-by-visit interaction, and age at baseline.

When an analysis of covariance (ANCOVA) model is used to analyze a continuous efficacy variable, the model will contain the main effects of treatment with baseline value and age at baseline added as covariates. For ANCOVA analysis on change from baseline to Week 52 endpoint, change from baseline to last observation during treatment period will be used if patients do not have Week 52 observation available.

Categorical comparisons between treatment groups will be performed using Fisher's exact tests or logistic regression where appropriate.

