#### **5.13.8.2. Skin Examination**

Skin color will be reported at baseline by using Fitzpatrick Scale Rating. The frequencies of the outcomes (I, II, III, IV, V, and VI) will be displayed by treatment group.

Any hypopigmentation will be assessed by location, percentage of body surface area involvement (BSA), degree (partial/decreased pigmentation to complete depigmentation), and other findings in or around the hypopigmentation area (e.g., redness or induration). A static physician's global assessment (sPGA) will be used to determine the subject's overall hypopigmentation severity at a given timepoint using a visual analog scale (VAS) ranging from 0 to 100. In addition, subjects noted to have evidence of hypopigmentation will be asked to record how bothersome they find the hypopigmentation on a VAS ranging from 0 to 100.

Frequency tables and summary statistics for the continuous parameters will be given by treatment group.

In order to display any changes/deteriorations during treatment, the following will be reported: number of subjects for whom no hypopigmentation was observed at baseline, but for whom at least once after randomization hypopigmentation was observed during treatment period; summary statistics for the difference of maximum value during treatment minus baseline value for percentage BSA of hypopigmentation, overall severity (sPGA) and "how bothered is the subject"; shift table of baseline vs. maximum value during treatment for degree of overall lesion severity.

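### The only change measure for visual acuity and intraocular pressure is the highest on-treatment reading minus one baseline reading; it overstates worsening from two examinations on and can separate 3 mg from placebo with no drug effect

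*SAP*

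**What the plan says.** SAP 5.13.8.3 first plans summary statistics for the continuous eye parameters, with acuity "scores expressed as logMAR calculated as the negative log (base 10) of the decimal scores", so a higher score is a worse one. It then adds "summary statistics for the difference of maximum value during treatment minus baseline value for left eye total visual acuity score", and the same for the right eye and for intraocular pressure in each eye. It gives no other change measure for these two parameters: no change by visit, no change to last visit, no model and no test.

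Baseline is a single reading. SAP 5.1 says that "baseline value is defined as last value available before or at Visit 3", and the Schedule of Activities (Protocol Section 2) has only one scheduled eye examination before dosing, at Visit 1. On-treatment examinations fall at Weeks 12, 32 and 52, and at early discontinuation (ED). Protocol 9.4.5.2 adds that patients with visual complaints "should be referred to the optometrist or ophthalmologist for unscheduled evaluation". The SAP does not say whether ED or unscheduled readings enter the maximum.

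Protocol 10.3.4 names eye examinations among the safety data, calls for comparisons of each dose with placebo, and states: "For continuous safety measurements, a change from baseline will be analyzed using an MMRM or an ANCOVA model".

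**The concern.** A maximum over several readings minus one reading is not an estimate of change. Even if nothing happens to the eye, measurement error alone pushes it upward, and the push grows with the number of examinations. For both measures, upward is the unfavourable direction.

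Two things are at stake. First, within an arm, the table can show an average loss of acuity and rise in pressure that did not occur. Second, between arms, the shift cancels only if patients had similar numbers of examinations. The eye is a stated safety interest: the Assessment Committee reviews unblinded eye data with an ophthalmologist (Protocol 9.4.5.2), and retinal disorders are among the adverse events of special interest (SAP Table LLCF.SAP.3). The SAP's other eye analysis, of treatment-emergent findings by Fisher's exact test, covers slit lamp, dilated fundus, colour vision, fundus photography and ocular coherence tomography. Acuity and pressure are not in it. Laboratory values, vital signs and ECGs all receive change from baseline by visit with ANCOVA (SAP 5.13.4 to 5.13.6); these two measures do not.

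**Working it through.** The plan states no figure for this statistic, so there is none to reproduce.

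**Inputs from the documents**
- One baseline reading (SAP 5.1; Protocol Section 2).
- k = 1 to 3 scheduled on-treatment readings, at Weeks 12, 32 and 52; one ED or unscheduled examination could add to k.
- Planned arms of about 167 placebo, 167 on 12 mg and 45 on 3 mg (Protocol 5.1). Allocation is 1:1:1 until about 45 per arm, then 1:1 for 12 mg and placebo (Protocol Synopsis).
- Follow-up cut short: "majority of the subjects would not have Week 52 observation due to early termination of the study" (SAP Section 3).

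**Assumed, not in the documents**
- Stable eye; each reading is a constant plus normal error with SD s, independent between readings.
- s from 1 to 3 mmHg for pressure and from 0.03 to 0.10 for logMAR.

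**Step 1: expected value in a stable eye.** The baseline error averages zero, so E[max of k readings − baseline] = s × E[max of k standard normals]. For k = 2 the factor is 1/√π = 0.564; for k = 3 it is 3/(2√π) = 0.846; for k = 4, by numerical integration, 1.029. By symmetry, the chance that the difference is positive is k/(k+1).

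| Examinations k | Expected result | Stable eyes shown as worse | Pressure, s = 1 / 2 / 3 mmHg | logMAR, s = 0.03 / 0.05 / 0.10 |
|---|---|---|---|---|
| 1 | 0 | 50% | 0 | 0 |
| 2 | 0.564s | 67% | 0.56 / 1.13 / 1.69 | 0.017 / 0.028 / 0.056 |
| 3 | 0.846s | 75% | 0.85 / 1.69 / 2.54 | 0.025 / 0.042 / 0.085 |
| 4 | 1.029s | 80% | 1.03 / 2.06 / 3.09 | 0.031 / 0.051 / 0.103 |

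A simulation of 1,000,000 eyes per k agrees with these factors.

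**Step 2: correlated errors.** If all readings, baseline included, have error correlation ρ, the factor is multiplied by √(1 − ρ). At ρ = 0.5 and k = 3: 0.846 × 0.707 = 0.598, so 0.60s.

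**Step 3: 3 mg against placebo.** All 3 mg patients enrolled while the 1:1:1 allocation was open. About 45 of the 167 placebo patients did so too; the other 122 enrolled later. If early enrollees have a examinations and later ones b, and e denotes the factors in Step 1, the difference with no drug effect is (122/167) × (e_a − e_b) × s = 0.7305 × (e_a − e_b) × s. The visit counts are illustrative:
- a = 3, b = 1: 0.7305 × 0.846 = 0.618s, or 1.24 mmHg at s = 2.
- a = 3, b = 2: 0.7305 × (0.846 − 0.564) = 0.206s, or 0.41 mmHg at s = 2.
- a = 2, b = 1: 0.7305 × 0.564 = 0.412s, or 0.82 mmHg at s = 2.

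**Step 4: per-visit change.** At any one visit the expected change in a stable eye is 0 whatever k is (simulated means of the last-visit change lie within 0.003s of 0), and half of stable eyes show a positive value.

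**The case against.** The strongest reply is that this is a worst-value safety display, labelled as such and additional to summaries of the observed values. No test, stopping rule or efficacy result uses it, and placebo is there to calibrate it. Much of that stands. The statistic affects neither type I error nor the primary endpoint, and a worst-value summary is a legitimate screen. Non-principal changes to methods may also be explained in the study report (Protocol 10.3.1, SAP 5.1).

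Three stronger readings are tempting, and the documents do not support them.
- A reader might infer that true mean changes cannot be recovered at all. The section also summarises observed values and does not confine them to one time point, so means may be comparable indirectly.
- A reader might infer that every arm must show worsening. With one on-treatment examination the bias is zero, and with most patients lacking Week 52, three scheduled examinations will be the minority case.
- A reader might infer that 12 mg against placebo is distorted. Those arms were allocated equally throughout, so early termination by itself shortens both alike.

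What the reply does not meet is that the maximum is the only change defined for these two measures, that no planned analysis compares them between arms, and that calibration by placebo needs matching examination counts, which the 3 mg arm probably lacks.

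**Conclusion.** The point holds as a gap in the safety reporting of two eye measures. Maximum minus a single baseline overstates worsening in stable eyes once there are two or more examinations: 0.56s for two and 0.85s for three with independent errors, 0.60s for three at an error correlation of 0.5. The direction and the growth with visits follow from the definition under exchangeable error. The mmHg and logMAR figures rest on assumed SDs and are illustrations.

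Between arms, 3 mg against placebo is the exposed comparison, at roughly 0.2s to 0.6s under the assumed visit counts. The documents give no examination counts, so the actual gap is unknown; that one is likely follows from early-only enrolment to 3 mg combined with early termination. 12 mg against placebo is little exposed unless discontinuation differs.

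A reader might extend this to the skin examination, where SAP 5.13.8.2 uses the same construction. The calculation does not carry over: hypopigmented body surface area is bounded at zero, and patients with a history of vitiligo or current post-inflammatory hypopigmentation are excluded (Protocol 6.2, criterion 19), so symmetric normal error around a stable level is not shown to apply.

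**What to change.** In SAP 5.13.8.3, for visual acuity and intraocular pressure:
1. Add change from baseline at each scheduled eye visit, per eye, compared with placebo by the ANCOVA already set out in SAP 5.2 (treatment, baseline value, age at baseline). This carries over Protocol 10.3.4.
2. Keep maximum minus baseline only as a supplementary worst-value display, with the number of on-treatment examinations per patient shown by arm beside it.
3. State whether ED and unscheduled examinations count towards the maximum.

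Do not swap the maximum for a count of patients whose maximum passes a threshold. That count has the same fault: under the model above, the share of stable eyes whose maximum exceeds baseline by more than 2s is 7.9%, 13.4% and 17.7% for one, two and three examinations.

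The cost is a short change of wording and a few extra tables from data already collected.

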#### **5.14. Safety Follow-up Visit**

Follow-up visit (Week 56) is not required for patients who discontinue study treatment early and who continue in the study unless study drug was discontinued within the last 4 weeks of the study.

Adverse events, concomitant medications, vital signs, and ECGs will be collected at these visits. These data will be summarized by treatment received during placebo-controlled treatment period.

#### **5.15. Protocol Violations**

Listings of subjects with significant protocol violations will be provided for the Full Efficacy population. The following list of significant protocol violations will be determined from the clinical database and from the clinical/medical group:

- Did not have an assessment of either the primary endpoint at any of the visits at which the scales were scheduled to be assessed.
- Protocol violations of inclusion/exclusion criteria.
- Had a study dosing algorithm violation (such as if subjects randomized to treatment A were given treatment B or subjects randomized to treatment A never received the assigned study drug.)
- Had unqualified raters or raters with substantial scoring errors for the co-primary measures.
- Was not compliant with regard to study drug.

The analyses for the primary objective will be repeated for the per protocol subject population.

#### **5.16. Interim Analyses and Data Monitoring**

An assessment committee (AC) will have the responsibility to review accumulating study data at a pre-specified interim analysis and make recommendations to protect the safety of subjects. The approved AC charter enumerates the roles of the AC members and the structure of their meetings. A statistical analysis plan (SAP) for analyses associated with the AC list out the specific analyses that the AC will review.

One scheduled interim analyses will be conducted during this study. The AC charter will specify the final details of the interim analyses. Only the AC is authorized to evaluate unblinded interim safety analyses. Study sites will receive information about interim results only if they need to know for the safety of their subjects.

### **5.16.1. Interim Analysis**

The objective of the interim analysis (IA) is to conduct a safety analysis. One safety interim analysis conducted by the AC is planned when data from approximately 105 qualified patients at 12 weeks and 75 patients through 24 weeks have been obtained. The AC may be asked to conduct additional safety interim analyses if safety concerns are observed during blinded safety monitoring. In the event that blinded safety monitoring uncovers an issue that needs to be addressed by unblinding at the group level, only members of the AC can conduct additional analyses of the safety data.

A limited number of pre-identified individuals may gain access to the unblinded PK/PD data, as specified in the unblinding plan, prior to the interim or final database lock. Information that may unblind the study during the analyses will not be reported to study sites or blinded study team until the study has been unblinded.

